7.7. Packaging and Labeling

The label for IP (Dara) will include manufacturer name, address and telephone number, the protocol number, IP name, dosage form, and strength amount of IP per container, lot number, expiry date (where

applicable), medication identification/kit number, dosing instructions, storage conditions, and required caution statements and/or regulatory statements as applicable. Additional information may be included on the label as applicable per local regulations.

7.8. Investigational Product Compliance

The investigator will document the number of capsules of POM issued to and returned by each subject at each study visit. The investigator will document the number of vials of DARA administered to each subject at each DARA administration visit. Overall, the investigator will also be responsible for documenting subject compliance for Dara, Pom and Dex.

8. CONCOMITANT MEDICATIONS AND PROCEDURES

8.1. Permitted Concomitant Medications and Procedures

Other therapies considered necessary for the subject's well-being may be administered at the discretion of the investigator. These therapies may include antibiotics, analgesics, antihistamines, or other medications and transfusions of RBC, platelets, or fresh frozen plasma given to assist in the management of complications associated with MM or its therapy. These therapies also include pre and post infusion medications required for the administration of DARA as per Section 8.2.

The prophylactic use of hematopoietic growth factors will be allowed throughout the study at the treating physician's discretion. Once allowed, the use of myeloid growth factors is encouraged when ANC is less than 1,000/ μ L at the discretion of the treating physician.

Subjects who met the ANC, hemoglobin, and platelet eligibility criteria due to growth factor treatment or platelet/blood transfusion received prior to the start of the screening period are acceptable. Platelet and RBC transfusions are also permitted during the study.

Adjunctive radiation therapy to a pathological fracture site or to treat bone pain is permitted. Subjects with myeloma-associated bone disease may receive bisphosphonate therapy prior to study entry, as well as other agents that may be used for myeloma-associated bone disease such as denosumab and teriparatide, unless such therapy is contraindicated. The use of bisphosphonates, as well as other agents for the treatment of myeloma-associated bone disease, is permitted throughout the study.

Thromboembolism prophylaxis: Low-dose aspirin, low molecular weight heparin, or other equivalent antithrombotic or anti-coagulant will be given to all subjects per Lenalidomide and Pomalidomide guidelines. The following therapies will be collected and recorded in the subject's Concomitant Medication eCRF page: Anti-infectious agents, anti-thrombotics, growth factors, and bisphosphonates or other agents used for the treatment of myeloma-associated bone disease. All procedures, including transfusions, will be collected and recorded in the subject's eCRF.

8.2. Prohibited Concomitant Medications and Procedures

Concomitant use of other approved or investigational anti-myeloma therapy within 14 days of Cycle 1 Day 1 or while the subject is taking study drug (study treatment phase) is prohibited. Subsequent anti-myeloma treatment should not be initiated prior to PD or study treatment discontinuation.

Chronic use of steroids (other than Dex) or any other immunosuppressive therapies is prohibited in this study without approval from the Medical Monitor.

Drugs known to prolong the QT corrected (QTc) interval should be avoided unless deemed medically necessary. See Appendix G for a comprehensive list of drugs known to prolong QTc.

8.3. Required Concomitant Medications and Procedures

Recent or active cancer is a recognized prothrombotic risk factor for increasing the risk of VTE.

Increased plasma viscosity related to monoclonal paraproteinemia has been implicated as a risk factor for VTE in MM subjects. Clinical studies have shown that thalidomide and Len in combination with Dex or other chemotherapeutic agents increase the risk of VTE (Baz, 2005; Weber, 2007). Aspirin has been reported to be effective in reducing the incidence of DVT in MM subjects treated with thalidomide or LEN (Baz, 2005).

For the current study, low-dose aspirin, low molecular weight heparin, or other equivalent antithrombotic or anti-coagulant will be given during the study to all subjects. Antithrombotic prophylaxis will be recorded on the eCRF.

Pre and post infusion medications required for the administration of Dara as per Section 8.2 will also be recorded on the eCRF. Subjects who develop symptomatic DVT will be assessed and diagnosed objectively by Doppler ultrasonography or a comparable method. Diagnostic algorithms are provided in Appendix A.

8.4. Management of Hepatitis B Virus Reactivation

Primary antiviral prophylaxis is permitted as per local standard of care. Per protocol, HBV DNA testing by PCR is mandatory for subjects at risk for HBV reactivation see Sections 5.4 and 5.5.

For subjects who are diagnosed with HBV reactivation while on treatment, study treatment should be interrupted until the infection is adequately controlled. If the benefits outweigh the risks, study treatment may be resumed with concomitant antiviral prophylaxis as per local standard of care. Consult a liver disease specialist as clinically indicated.

9. STATISTICAL ANALYSIS

9.1. Overview

In general, continuous data will be summarized by descriptive statistics, including number of patients, mean, standard deviation, median, minimum, and maximum. Categorical data will be summarized by the number and percentage of patients. Unless otherwise specified, data will be summarized by treatment arm. A detailed description of analysis methods will be provided in the statistical analysis plan.

9.2. Sample Size and Power Considerations

Phase 1b of the study will follow a standard 3 + 3 dose escalation design as described in Section 7.4. With two dose levels, the study will need between 3 and 12 patients depending on toxicities. Patients will be considered evaluable in phase 1b for MTD assessment provided that they have not missed any of their doses of ATRA in Cycle 1, or have had a DLT. Patients who are not considered evaluable as defined above will be replaced.

For the phase 2 portion:

Approximately 20 patients who fulfill the eligibility criteria of the protocol will be enrolled. The phase 2 study will use a Simon 2-stage minimax design, whereby 10 patients will be accrued in the first stage, and ORR assessed, before moving to the next stage. If ≥ 3 objective responses are observed in the first stage, the study will proceed to the next stage; and an additional 10 patients will be accrued. If there are 8 or

more responses among the 20 patients, the combination will be declared worthy for further evaluation. The null hypothesis that the true response rate is 25% or less will be tested against a one-sided alternative of 48% or higher at the one-sided type I error of 0.10. This design yields a type I error rate of 0.096 and power of 0.806 when the true response rate is 48%. The probability of early stopping due to futility is approximately 52.0%.

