4. OVERALL STUDY DESIGN

4.1. Study Design

This is a multicenter, open label study of Dara+Pom+Dex combined with ATRA in patients progressing on a Dara+Len+Dex regimen. The study is expected to enroll up-to a maximum of 42 patients (20-32 subjects previously exposed to Dara + Len + Dex; 10-22 subjects previously exposed to Dara + Pom + Dex)..

The phase 1b portion will follow a standard 3+3 dose escalation design with two dose levels and up to 12 patients. Under this design, the investigators will evaluate dose levels as follows:

- Dose level 1 - ATRA 35.5 mg/m²/day on days -2,-1 and 1 on a 28-day cycle in combination with daratumumab, pomalidomide, and dexamethasone
- Dose level 2 – ATRA 45 mg/m²/day on days -2,-1 and 1 on a 28-day cycle in combination with daratumumab, pomalidomide, and dexamethasone

During the dose-escalation phase and after the first cycle, and after the first cycle, patients who have not experienced a DLT, have not shown signs of PD, and in the opinion of the investigator would continue to benefit from treatment may receive additional cycles of treatment.

The phase 2 portion will be conducted in two stages. In the first stage, 10 patients will be accrued. A safety and efficacy analysis will be conducted 3 months after accrual of the first 10 patients. If there are 2 or fewer responses in these 10 patients, the study will be stopped due to futility. If the stopping rules for safety are met, then the study will be stopped due to toxicities. Otherwise, accrual will continue for a maximum of 42 in phase 1b and phase II combined.

During 28-day treatment cycles, patients will receive Dara 1800 mg subcutaneous (SC) at their current dose upon enrollment onto the study depending on their cycle. (If they are on cycles 1-2 then they will receive Dara 1800 mg SC days 1,8,15,22; if they are on cycles 3-6 they will receive Dara 1800 mg SC days 1 and 15; if they are on cycle 7 or beyond they will receive Dara 1800 mg SC on day 1).

Pomalidomide will be administered at the patient's currently tolerated dose (4,3, or 2 mg po daily) on days 1-21. For patients progressing on daratumumab, lenalidomide, and dexamethasone, the starting dose of pomalidomide will be 4 mg per standard of care.

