7.4. Dose Escalation for ATRA and Study Stopping Rules

The phase 1b portion of the study will follow a 3+3 dose escalation design to evaluate Dose Level 1 (35.5 mg/m²/day) followed by Dose Level 2 (45 mg/m²/day) of ATRA in combination with Dara + Pom + dex for DLTs and to determine the MTD for further assessment in phase 2.

Patients will be enrolled in cohorts of 3 and assessed for DLTs over a 28-day period. In each dose level, the second and third patients can be dosed concurrently once the first patient in the cohort has gone uneventfully through the Day 8 visit. If it is necessary to enroll more than 3 patients in a cohort, and there have not been any TEAEs in the previously dosed patients in that cohort, these new patients can be enrolled concurrently.

If none of the patients in a cohort of 3 patients exhibits a DLT during the 28-day cycle, then the dose may be escalated for the next cohort of 3 patients. If 1 patient in a cohort of 3 patients exhibits a DLT, then that cohort will be expanded to a total of 6 patients. If 2 or more patients in a cohort of 3 patients exhibit a DLT, then that cohort will be deemed to have exceeded the MTD, and dose escalation will be stopped.

If the dose cohort below that at which the MTD is exceeded has enrolled only 3 patients, then 3 additional patients will be enrolled at that dose level. The MTD is defined as the highest dose with a cohort of 6 patients having no more than 1 patient with a DLT. For the cohort expansion, 3 patients will only be enrolled sequentially if a DLT observed in the initial cohort was life-threatening, it appeared before the Day 8 visit and/or the clinical team consider that based on the observed toxicity is prudent to stagger the enrollment. Sequential enrollment is not required in case of de-escalation or if no DLT was observed in the first 3 patients in a cohort.

During phase 1b dose escalation, patients who miss one or more scheduled Cycle 1 doses of ATRA for reasons other than a DLT will be replaced.

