Hyperglycemia \geq Grade 3	Decrease dose by one dose level. Treat with insulin or oral hypoglycemic agents as needed.
Acute pancreatitis	Discontinue subject from Dex treatment regimen.
Other \geq Grade 3 Dex-related adverse Events	Stop Dex dosing until the adverse event resolves to \leq Grade 2. Decrease by one dose level when Dex dosing is resumed.

^a If recovery from toxicities is prolonged beyond 14 days, then the dose of Dex will be decreased by one dose level when dose is restarted.

Table 7: Dexamethasone Dose Reduction Steps

Dose Level	≤ 75 years old	>75 years old
Starting Dose	40 mg	20 mg
Dose Level -1	20 mg	12 mg
Dose Level -2	10 mg	8 mg

ATRA will be administered in a divided dose of twice daily as an oral formulation at 35 mg/m²/day for Phase with dose escalation to 45mg/m²/day for 3 days. The dose expansion phase will be at the 45 mg/m²/day dose after safety and efficacy has been evaluated. The first administration of ATRA will be given in the morning, two days before the scheduled Dara infusion. The last administration of ATRA will be given in the evening of the day that Dara was administered (days -2, -1, and 1; day 1 is the day of Dara infusion).

ATRA-related toxicities

Subjects will be monitored for neurological symptoms and nutritional status. If Wernicke's encephalopathy is suspected, ATRA should be interrupted and parenteral thiamine should be initiated.

Pseudotumor cerebri

This complication has been mainly reported in patients aged <20 years and is characterized by presence of severe headache with nausea, vomiting, and visual disorders.

It is recommended to temporarily discontinue ATRA treatment and to administer opiates. As soon as the symptoms and the patient clinical conditions improve, the treatment with ATRA will be resumed at 50% of the previous dose during the first 7 days after the amelioration of pseudotumor cerebri. Thereafter, in absence of worsening of the previous toxicity, ATRA should be resumed at full dosage.

Table 8: ATRA Dose Reduction Steps

Dose Level	ATRA Dose reduction
Dose Level 2	45 (mg/m ²)
Dose Level 1 (Phase 1b starting dose)	35.5 (mg/m ²)
Dose Level -1	25 (mg/m ²)
Dose Level -2	20 (mg/m ²)

- ATRA will be discontinued for any Grade 4 non-hematologic toxicity.
- In the case of Grade 3 toxicity, ATRA should be held until the toxicity resolves to Grade ≤ 1 or baseline, at which time it may be resumed at a reduced dose.

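### For patients without a DLT, phase 1b evaluability and replacement depend only on Cycle 1 ATRA doses, which are finished on Day 1 of a 28-day DLT window

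*Combined protocol and SAP*

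**What the plan says.** Section 9.2 counts patients as "considered evaluable in phase 1b for MTD assessment provided that they have not missed any of their doses of ATRA in Cycle 1"; the same sentence also admits anyone who had a DLT. It continues: "Patients who are not considered evaluable as defined above will be replaced". Section 7.4 applies the same trigger during escalation: "patients who miss one or more scheduled Cycle 1 doses of ATRA for reasons other than a DLT will be replaced".

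Section 4.1 schedules "ATRA 35.5 mg/m²/day on days -2,-1 and 1 on a 28-day cycle" for dose level 1, with the same days for dose level 2. Section 7.5 puts the last dose on the evening of the daratumumab day ("days -2, -1, and 1; day 1 is the day of Dara infusion"). The Protocol Summary and another paragraph of Section 4.1 number that day 0, but the last dose falls on that evening either way.

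On the observation period, Section 7.4 says: "Patients will be enrolled in cohorts of 3 and assessed for DLTs over a 28-day period". Section 7.3 counts DLTs for escalation up to dosing on Cycle 2 Day 1. The MTD (Section 7.4) is the highest dose at which at most one of six patients has a DLT. The phase 1b objective (Section 2) is the safety and toxicity profile of daratumumab, pomalidomide, dexamethasone and ATRA together.

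**The concern.** A patient without a DLT carries information about the dose only if the patient was treated and observed long enough for a DLT to appear. Here the sole test for such a patient is passed by the evening of Day 1, with nearly the whole window still to run. Two kinds of patient can pass it without being informative:

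- **Observation incomplete:** the patient withdraws consent, is lost or dies of myeloma soon after Day 1.
- **Exposure incomplete:** the patient stops early and receives little of the planned combination, although adverse events are still collected.

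Under the literal rule both stay evaluable, are not replaced and enter the cohort as zeros. At stake are the decision to escalate and the MTD, which is carried into phase 2. With three or six patients per level, one such zero matters.

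**Working it through.** **1. The plan's own figure.** Section 9.2 gives 3 to 12 patients for two dose levels. Following the rules of Section 7.4:

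- two or more DLTs in the first three at level 1: stop at 3;
- one in three, expansion to six, then a second DLT: stop at 6;
- level 1 passed, two or more DLTs in the first three at level 2, level 1 filled to six: 6 + 3 = 9;
- both levels filled: 6 + 6 = 12.

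The range of 3 to 12 reproduces. It allows for replacements only under the ATRA-dose rule.

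**2. The timeline.** ATRA is given twice daily on three days, so 2 × 3 = 6 doses, the last on the evening of Day 1. Pomalidomide runs on days 1–21 (Section 4.1). The DLT window runs 28 days, or to Cycle 2 Day 1. Section 7.3 includes DLTs that cannot be seen in the first days, such as Grade 4 neutropenia persisting beyond a week, or a delay to Cycle 2 of more than three weeks.

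**3. The rule applied to DLT-free patients.**

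| Patient | All ATRA taken | Evaluable under 9.2 | Replaced |
|---|---|---|---|
| Completes the window on treatment | yes | yes | no |
| Lost, withdrawn or dead of myeloma soon after Day 1 | yes | yes | no |
| Stops early with little combination treatment, still followed | yes | yes | no |
| Missed an ATRA dose | no | no | yes |

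The rule cannot tell the first three rows apart.

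**4. Effect on the MTD criterion.** Let p be the true DLT rate over the window and k the number of the six who are counted but cannot show a DLT. With m = 6 − k patients at risk,

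P(at most 1 DLT) = (1 − p)^m + m·p·(1 − p)^(m − 1).

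At p = 1/3:

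- k = 0: (64 + 192)/729 = 0.351
- k = 1: (32 + 80)/243 = 0.461
- k = 2: (16 + 32)/81 = 0.593

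| p (assumed) | k = 0 | k = 1 | k = 2 |
|---|---|---|---|
| 0.25 | 0.534 | 0.633 | 0.738 |
| 1/3 | 0.351 | 0.461 | 0.593 |
| 0.40 | 0.233 | 0.337 | 0.475 |
| 0.50 | 0.109 | 0.188 | 0.312 |

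**5. Effect on escalation.** P(no DLT in the first three) = (1 − p)^(3 − k). At p = 1/3 it is 8/27 = 0.296 with all observed and 4/9 = 0.444 with one lost but counted. At p = 0.40 it is 0.216 and 0.360.

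**6. What the figures bound.** They give a lost patient no chance at all of an observed DLT. A patient who is under-exposed but followed, or observed for part of the window, has a chance between 0 and p. One such patient therefore gives a value between the k = 0 and k = 1 columns, for example between 0.351 and 0.461 at p = 1/3.

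**The case against.** **The 28-day intent is written down.** Section 7.4 assesses patients over 28 days, escalates only if none of three has a DLT in that cycle, and holds the next cohort until safety data are available for every patient in the current one. That an early loss counts as DLT-free follows from the rules but is not stated in words. This stands as evidence of intent. It does not make an incompletely observed patient non-evaluable or replaceable. Section 7.3 asks for completed Cycle 1 assessments before intrapatient escalation; no such condition is attached to MTD evaluability.

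**Stopping treatment is not loss of observation.** Sections 5.2 and 10.1 collect adverse events for 30 days after treatment ends, so a patient who stops on Day 5 for progression is followed to about Day 5 + 30 = 35, past the window. This is right. Early progression is a problem of exposure, and the k = 1 and k = 2 columns do not measure it.

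**ATRA is the only escalated drug.** True, and daratumumab is planned on Day 1 alone for patients at cycle 7 or beyond, so absence of later daratumumab need not mean under-treatment. An exposure condition should therefore be a share of what was planned for that patient. How large a share is a design choice.

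**Losses may be few, and there are backstops.** Entry requires a life expectancy above three months and ECOG 0–2. DLT-like events in later cycles bear on whether the MTD is suitable (Section 7.3), a DLT incidence above 40% stops the trial (Section 9.4), and the DSMC reviews quarterly (Section 11.3). These limit the harm but do not correct the count on which the MTD is declared.

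**A stronger reading that does not hold.** A reader might infer that the rule also favours the dose from the other side, by replacing patients who missed ATRA because of toxicity short of a DLT. It does not. A patient who misses ATRA and has a DLT remains evaluable, so only DLT-free patients are replaced. Replacement removes a certain zero and brings in someone who can have a DLT. Keeping that zero would add the same dilution as in the working (0.351 to 0.461 at a rate of 1/3). These patients are also not hidden: Section 7.4 reviews all treated patients, and Section 9.4 keeps them in the safety population.

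**Conclusion.** The gap is real and lies in the wording. Sections 9.2 and 7.4 let a DLT-free patient count towards the MTD on a condition met on Day 1, without requiring the DLT window to be completed or any minimum of the other three drugs to be received. Followed literally, this can only make a dose look safer.

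With one of six unobserved but counted, the chance of meeting the MTD criterion rises by 0.110 at a true rate of 1/3 (0.461 − 0.351) and by 0.104 at 0.40 (0.337 − 0.233). With two, it rises by 0.242 (0.593 − 0.351; both cohort probabilities at 1/3) and 0.242 (0.475 − 0.233; at 0.40). These sizes rest on assumed DLT rates, on assumed losses of one or two in six (17% or 33%), and on no observable DLT in the lost patients. The documents support none of these as a forecast, so the figures show sensitivity and are not an estimate of bias. For patients who stop early but are still followed, the effect is smaller and is not quantified here.

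**What to change.** Use one definition in both Section 9.2 and Section 7.4. A patient is DLT-evaluable if either:

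- (a) a DLT occurs at any time in the window; or
- (b) all Cycle 1 ATRA doses were taken, a minimum share of that patient's planned Cycle 1 combination treatment was received (unless withheld for toxicity), and follow-up reached the end of the DLT window without a DLT.

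Replace everyone else. The study team should set the minimum share in advance and state whether the window ends at Day 28 or at Cycle 2 Day 1 dosing, since Sections 7.4 and 7.3 use both. The existing replacement of DLT-free patients who missed ATRA can stay.

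The text should be in force before any cohort is judged, because redefining evaluability once DLTs are known would undermine the MTD decision. The cost is a wording amendment to two sections and possibly one or two replacement patients in phase 1b.

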This Simon's two-stage design yields a type I error rate of 0.095 and power of 0.802 when the true response rate is 48%. The probability of early stopping due to futility is approximately 49.2%.

Primary Analysis

After a maximally 42 patients are enrolled in the phase 1b and phase 2 portions combined, a primary interim efficacy analysis and the second safety analysis will be conducted. The subset safety analysis will be also descriptively performed based on the previous exposure groups (Dara + Len + Dex or Dara + Pom + Dex).

Overall response rate (ORR) and stringent complete response (sCR)/CR/near CR (nCR) according to IMWG criteria will be determined and corresponding 2-sided 80% exact binomial confidence interval will be calculated. The subset ORR analysis will be also performed based on the previous exposure groups (Dara + Len + Dex or Dara + Pom + Dex).

The Kaplan-Meier (KM) method will be used to estimate the time-to-event endpoints such as time on study (TOS), duration of response (DOR), time to progression (TTP), progression-free survival (PFS) and overall survival (OS) distributions. The subset time-to-endpoint outcome analysis will be also performed using the KM method based on the previous exposure groups (Dara + Len + Dex or Dara + Pom + Dex).

Adverse events and tolerability from all subjects who receive at least one dose of study drug will be evaluated for safety and tolerability. Data will be tabulated to examine the frequency.

Study Sites

1. Hackensack University Medical Center - John Theurer Cancer Center - Hackensack, NJ
2. Georgetown-Lombardi Cancer Center - Washington, DC

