3. STUDY ENDPOINTS

Primary Endpoints:

Phase 1b: The percentage of patients with treatment emergent adverse events (TEAEs) overall and per dose level.

- Patients with DLTs at each dose level.
- Patients with Grade ≥ 3 TEAEs
- Patient with serious adverse events (SAEs)
- Patients who discontinue because of TEAEs
- Patients with dose modifications (delays, interruptions, dose reductions)
- Clinically significant laboratory values

Phase 2: ORR as defined by IMWG criteria (subjects progressing on Dara + Len + Dex)

Secondary Endpoints:

- 1) ORR as defined by IMWG criteria (subjects progressing on Dara + Pom + Dex)
- 2) Rate of CR, sCR, or nCR
- 3) Rate of VGPR
- 4) TTP
- 5) DOR
- 6) PFS using Kaplan Meier
- 7) OS using Kaplan Meier

Exploratory Endpoints:

Explorative endpoints of samples collected before, during and after treatment with Dara + ATRA, + Pom + Dex and include but are not limited to the following:

- 1) Gut Microbiome analysis
- 2) Immune cell subset analyses
- 3) Analyses of cytokine, chemokine, inflammatory/anti-inflammatory and bacterial translocation markers
- 4) Basic peripheral blood laboratory variables
- 5) Genetic and epigenetic profiles

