9.3. Efficacy Analysis

The primary efficacy parameter is ORR by IMWG criteria. The ORR will be evaluated using 2-sided 80% exact binomial confidence intervals. The rate variables such as CR, sCR, nCR, and VGPR will be evaluated using 2-sided 80% exact binomial confidence intervals.

The distribution of time-to-event response including DOR, TOS, PFS, and OS will be estimated by Kaplan-Meier methodology. The medians of these time-to-event efficacy responses, if available, and their 2-sided 95% CI, will be reported. In addition, the proportions of patients with events at selected time points, together with their 2-sided 95% CI will be presented. The calculations will be performed based on a fixed sample, single-stage design. Time to event analysis will be based on all data combined.

Exploratory endpoints including biomarkers, microbiome, blood variables, and exosome will be summarized descriptively.

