9.5. Interim analysis

The first efficacy analysis for study futility will be assessed 3 months after 10 subjects are enrolled.

This study uses a Simon 2-stage minimax design. Interim analysis will be performed 3 months after 10 subjects are enrolled. If 2 or fewer of those 10 patients have a response, the study will be discontinued after Part 1 due to futility.

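### The phase 2 primary endpoint is ORR after Dara+Len+Dex, but the Simon counts, futility stop and primary ORR name no prior regimen; a Dara+Len+Dex-only cohort looks intended but is nowhere stated

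*Combined protocol and SAP*

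**What the plan says.** **Endpoint.** Section 3 restricts the primary endpoint to one prior regimen: "Phase 2: ORR as defined by IMWG criteria (subjects progressing on Dara + Len + Dex"). Section 2 and the Protocol Summary word the primary objective the same way. ORR in patients progressing on Dara+Pom+Dex is listed separately as secondary.

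**Decision rules.**
- Section 9.2: "Approximately 20 patients who fulfill the eligibility criteria of the protocol will be enrolled". The design has 10 patients in stage 1, continues on 3 or more responses, adds 10, and succeeds on 8 or more of 20 (25% against 48%). Inclusion criterion 3 in Section 6.2 accepts either prior regimen.
- Section 4.1: "A safety and efficacy analysis will be conducted 3 months after accrual of the first 10 patients". The trial stops on 2 or fewer responses. "Otherwise, accrual will continue for a maximum of 42 in phase 1b and phase II combined".
- Section 9.5: "The first efficacy analysis for study futility will be assessed 3 months after 10 subjects are enrolled".
- Section 9.3: "The primary efficacy parameter is ORR by IMWG criteria". No population is attached.
- Protocol Summary, Primary Analysis: "After a maximally 42 patients are enrolled in the phase 1b and phase 2 portions combined, a primary interim efficacy analysis" is run. ORR by prior regimen appears there as a subset analysis.

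**Accrual.** Section 4.1 gives a maximum of 42, made up of "20-32 subjects previously exposed to Dara + Len + Dex; 10-22 subjects previously exposed to Dara + Pom + Dex". Phase 1b takes up to 12.

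**Text pointing to one regimen.** The first sentence of Section 4.1 and the Study Design paragraph of the Protocol Summary describe only patients who progressed on Dara+Len+Dex.

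**Phase 1b.** Section 9.4 refers to 20 patients expected to be treated across phase 1b and phase 2 at one dose.

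**The concern.** The population in the primary endpoint and the population counted by the decision rules are not the same on the page. If staff apply the rules as printed, the first 10 and then the first 20 eligible patients drive the stop and the go/no-go decision, whatever they received before. That answers a question about a mixture set by order of accrual.

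The two groups could plausibly respond differently. Under Section 4.1, patients coming from Dara+Len+Dex start pomalidomide together with ATRA, while patients coming from Dara+Pom+Dex stay on pomalidomide and add ATRA. If the second group responds less often, a regimen that works in the primary population could be stopped or rejected. If the ambiguity is resolved only after responses are known, the choice of who counts is open to the data.

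**Working it through.** **1. Reproduce Section 9.2 for a single population.** With X1 and X2 each Binomial(10, p):
- P(stop) = P(X1 ≤ 2)
- P(success) = Σ over x = 3 to 10 of P(X1 = x) · P(X2 ≥ 8 − x)

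At p = 0.25, P(stop) = 0.0563 + 0.1877 + 0.2816 = 0.526 (stated: about 52.0%) and P(success) = 0.0956 (stated 0.096). At p = 0.48, P(stop) = 0.0702 and P(success) = 0.8059 (stated 0.806). Apart from the small gap in the early-stopping figure, the design is sound for one homogeneous population.

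**2. What the accrual totals imply.**
- 20 + 10 + 12 = 42, the maximum.
- 20 + 12 = 32 and 10 + 12 = 22, the two upper limits.

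These fit a Dara+Len+Dex cohort of 20, a Dara+Pom+Dex cohort of 10 and 12 phase 1b patients of either kind. A mixed phase 2 of 20 gives 32 in all, and one of 28 gives 40; neither is 42. This is an inference, and no passage states it.

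**3. The literal rule on a mixture.** Let m of each 10 patients be Dara+Pom+Dex with ORR q, and the rest Dara+Len+Dex at 48%. Each stage total is then Binomial(10 − m, 0.48) + Binomial(m, q), and the step 1 formulas apply to that sum. Neither m nor q is in the documents. At the full 42 the ranges allow 10/42 = 24% to 22/42 = 52% Dara+Pom+Dex, so m = 2 to 5 is used. For q, the range runs from the 9.2 null (25%) to equality (48%).

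| q | m per 10 | Power | Wrongful futility stop |
|---|---|---|---|
| 25% | 2 | 0.68 | 11% |
| 25% | 5 | 0.44 | 22% |
| 40% | 2 | 0.77 | 8% |
| 40% | 5 | 0.70 | 11% |
| 48% | any | 0.81 | 7% |

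**4. The Protocol Summary prints a different Simon design**, also without a regimen: stop on 4 or fewer of 12, succeed on 12 or more of 28, 30% against 50%. Its stated figures are 0.095, 0.802 (at 48%) and 49.2%.

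| Stop rule | Type I error (30%) | Early stop (30%) | Power at 50% | Power at 48% |
|---|---|---|---|---|
| 4 or fewer (printed) | 0.078 | 72.4% | 0.730 | 0.665 |
| 3 or fewer | 0.095 | 49.2% | 0.802 | 0.740 |

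The stated figures therefore need a stop at 3 or fewer and a 50% rate. As a Dara+Len+Dex-only cohort, with 10 Dara+Pom+Dex and 12 separate phase 1b patients, this design needs 28 + 10 + 12 = 50 places against a maximum of 42.

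**The case against.** The best defence is that the intent can be read from the document. Section 3 already restricts the primary endpoint, so Section 9.3 need not repeat it. The first sentence of Section 4.1 and the Protocol Summary's Study Design paragraph describe Dara+Len+Dex progressors only. The accrual arithmetic fits a Dara+Len+Dex cohort of 20 exactly. Section 9.1 leaves analysis detail to an SAP, and ORR by prior regimen will be reported in any case.

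Much of this stands as evidence of intent, but it does not settle the rule. The sentence after the opening of Section 4.1, the Study Population paragraph and Section 6.1 all enrol 10 to 22 Dara+Pom+Dex patients. The stop and success counts are fixed in the protocol itself, and reporting the subset ORR does not say which patients drive them.

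A reader might go further in three ways that the documents do not support:
- **That power is 0.58.** This comes from applying the literal rule to the first 20 of 30 phase 2 patients, 20 of them Dara+Len+Dex, with a Dara+Pom+Dex ORR of 25%. The 20 + 10 split belongs to the reading under which the rule counts Dara+Len+Dex only and no power is lost, and the 25% is assumed.
- **That type I error is inflated.** That needs a higher ORR after Dara+Pom+Dex, which the documents give no reason to expect.
- **That phase 1b patients must be left out of the 20.** Section 9.4 suggests that those at the chosen dose may count, so this is a choice for the sponsor.

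**Conclusion.** The point holds as a mismatch between the primary endpoint and the rules that decide it. Followed as written, the futility and success rules test a mixture. The documents do not show that a mixture was intended, and the weight of the text and totals favours a Dara+Len+Dex-only cohort of 20. Under that reading the 0.096 and 0.806 apply unchanged.

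Under the literal reading they apply to the primary hypothesis only if the two groups share one ORR. The loss in the illustration runs from none to a power of 0.44, and depends wholly on an assumed Dara+Pom+Dex ORR and an assumed mix. Even with equal rates, the population tested is not the one declared.

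It should be settled before the interim, because it determines whether the trial stops. The conflict between the two Simon designs is a separate defect that would exist whatever the prior regimen; it is noted here because both must be resolved in the same sentences.

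**What to change.** 1. State in Sections 4.1, 9.2, 9.3 and 9.5 and in the Protocol Summary that both Simon stages, the futility stop, the success rule and the primary ORR with its 80% CI count only patients who progressed on Dara+Len+Dex. Report Dara+Pom+Dex ORR separately as secondary and pooled ORR as supportive.
2. State before the interim whether phase 1b patients treated at the phase 2 dose count toward the 20. Reconcile Section 9.4 with that choice, and say how the 20-32 and 10-22 ranges are built.
3. Separately, keep one Simon design in the Protocol Summary and Section 9.2, with a stop rule and operating figures that belong to it.

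**Cost.** With the 9.2 design and phase 1b patients counted separately, the change is wording only: 20 + 10 + 12 = 42 already holds. If phase 1b patients count toward the 20, that breakdown counts them twice and the ranges need restating. If the 28-patient design is kept with separate phase 1b patients, the total of 50 exceeds the maximum by 8, so the ranges or the maximum must change.

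The interim would wait for the 10th Dara+Len+Dex patient. If 20 and 10 patients arrive in random order, that patient is on average number 10 × 31/21 = 14.8 in phase 2. At 42 patients in 24 months (1.75 a month), the delay is (14.76 − 10)/1.75, about 2.7 months. This is a rough figure: the mix is assumed, and the rate is averaged over the whole trial, including the phase 1b cohort waits.
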